6.1.4 Adverse Event Collection Period

All adverse events reported from the time of study drug administration until 30 days following discontinuation of study drug administration have elapsed will be collected, whether solicited or spontaneously reported by the subject. In addition, serious adverse events and protocol-related nonserious adverse events will be collected from the time the subject signed the study-specific informed consent.

Adverse event information will be collected as shown in [Figure 5](#).

Figure 5. Adverse Event Collection

Additionally, in order to assist the adjudication process, additional information on any potential MACE will be collected, if applicable.

In case of any of the following reported events, an appropriate supplemental cardiovascular events eCRF should be completed:

- Cardiac events;
- Myocardial infarction or unstable angina;

- Heart failure;
- Cerebral vascular accident and transient ischemic attack.

In case of a reported AE of herpes zoster, or a non-cardiac, non-CNS embolic or thrombotic event, the respective Supplemental AE eCRF should be completed.

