In order to minimize missing data for efficacy and safety assessments, subjects who prematurely discontinue study drug treatment should continue to be followed for all regularly scheduled visits as outlined in the Study Activities daily, unless they have decided to discontinue the study participation entirely (withdrawal of informed consent). Subjects should be advised on the continued scientific importance of their data even if they discontinue treatment with study drug early.

If a subject prematurely discontinues study participation (withdrawal of informed consent), the procedures outlined for the Premature Discontinuation Visit must be completed as soon as possible, preferably within 2 weeks.

A final telephone visit will occur for all subjects, approximately 30 days after the last dose of study medication to determine the status of any ongoing AEs/serious AEs (SAEs) or the occurrence of any new AEs/SAEs.

All attempts must be made to determine the date of the last study drug dose and the primary reason for premature discontinuation or study participation. The information will be recorded on the appropriate eCRF page. However, these procedures should not interfere with the initiation of any new treatments or therapeutic modalities that the investigator feels are necessary to treat the subject's condition. Following discontinuation of the study drug, the subject will be treated in accordance with the investigator's best clinical judgment, irrespective of whether the subject decides to continue participation in the study.

For subjects that are considered lost to follow-up, reasonable attempts must be made to obtain information on the final status of the subject. At a minimum, two phone calls must be attempted and one certified letter must be sent and documented in the subject's source documentation.

Subjects who discontinue the study prematurely will not be replaced.

COVID-19 Pandemic-Related Acceptable Protocol Modification

During the COVID-19 pandemic, it has been necessary to employ mitigation strategies to enable the investigator to ensure subject safety and continuity of care. Acceptable mitigation strategies are identified and included in Section 5.3.1.1 and [Appendix C](#) and [Appendix E](#).

The investigator should contact the sponsor medical contact before discontinuing a subject from the study for a reason other than "planned per protocol," to ensure all acceptable mitigation steps have been explored.

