All AEs leading to early termination of study drug will be presented in listing format.

The adverse events of special interest (infection, opportunistic infection, and gastrointestinal perforations, malignancies and drug related hepatic disorders) will be specified in the SAP.

A listing by treatment group of treatment-emergent AEs grouped by SOC and MedDRA preferred term with subject ID numbers will be generated.

The post-treatment AEs will be summarized in the same way as the treatment-emergent AEs described above.

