The Work Productivity and Activity Index assesses the impact of the condition on work productivity losses and impairment in daily activity. WPAI has six items covering four domains: (1) Absenteeism (work time missed), measured as the number of hours missed from work in the past 7 days due to a condition related problems. Scores are expressed as impairment percentages, adjusting for hours actually worked according to the WPAI scoring algorithm; (2) Presenteeism (impairment at work/reduced on-the-job effectiveness), measured as the impact of the condition on productivity while at work (i.e., reduced amount or kind of work, or not as focused as usual). Responses are recorded on a 0 – 10 Likert scale (where, 0 = no effect of UC on work and 10 = severe impact of UC while at work); (3) Productivity loss (overall work impairment), measured as the sum of hours missed due to condition (i.e., absenteeism) and number of hours worked with impairment (i.e., product of number of hours worked and presenteeism); and (4) Activity impairment (i.e., activities other than paid work like work around house, cleaning, shopping, traveling, studying), recorded and scored in the same way as presenteeism. Higher numbers indicate greater impairment and less productivity.³³

UC-SQ – Ulcerative Colitis Symptoms Questionnaire

The Ulcerative Colitis Symptoms Questionnaire (UC-SQ) is a UC-specific instrument composed of 17 items. UC-SQ was developed to assess UC related gastrointestinal symptoms (e.g., frequent bowel movements, abdominal pain, cramping) and non-gastrointestinal symptoms (e.g., joint pain and sleep difficulties). Each symptom item 1 - 9 can be responded on Likert-type of options such as (i) Not at all: 0 points; (ii) A little bit: 1 point; (iii) Somewhat: 2 points; (iv) Quite a bit: 3 points; (v) Very much: 4 points. Each symptom item 10 - 17 can be responded on Likert-type of options such as (i) Never: 0 points; (ii) Rarely: 1 point; (iii) Sometimes: 2 points; (iv) Often: 3 points; (v) Always: 4 points. Overall symptom scores are calculated by combining ratings of the individual items, with higher scores indicating greater severity.

HCRU – Health Care Resource Utilization

Health Care Resource Utilization data on number of all-cause and UC-related hospitalizations and surgeries will be collected through subject Administration module SAE supplemental Page.

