8.6 Additional Efficacy Analyses

Additional efficacy endpoints are defined in Section 3.3.

The estimands corresponding to the additional efficacy endpoints are defined for each of the binary additional endpoints as follows: difference in percentage of subjects achieving binary endpoints regardless of premature discontinuation of study drug and without use of

UC-related rescue medications (See Section 8.2.2) in the upadacitinib 15 mg QD, upadacitinib 30 mg QD and placebo groups in the ITT_A population.

The estimands corresponding to the additional efficacy endpoints are defined for each of the continuous additional endpoints as follows: difference in mean change from baseline regardless of premature discontinuation of study drug and if subjects would not use UC-related rescue medications (See Section 8.2.2) in the upadacitinib 15 mg QD, upadacitinib 30 mg QD and placebo groups in the ITT_A population.

The estimands corresponding to UC-related hospitalization and surgery incidence rates is as follows: difference in the incidence rate through Week 52 regardless of premature discontinuation of study drug or use of UC-related rescue medications in the upadacitinib 15 mg QD, upadacitinib 30 mg QD and placebo groups in the ITT_A population.

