9.2.2 Adverse Event Overview

An overview of AEs will be presented consisting of the number and percentage of subjects experiencing at least one event for each of the following AE categories:

- Any TEAE
- Any TEAE related to study drug according to the investigator
- Any severe TEAE
- Any serious TEAE
- Any TEAE leading to discontinuation of study drug
- Any TEAE leading to death
- TEAEs of Special Interest (as defined in [Appendix B](#))
- All deaths

- Deaths occurring \leq 30 days after last dose of study drug
- Deaths occurring $>$ 30 days after last dose of study drug

In addition, an overview of AEs per 100 patient-years of study exposure will be presented for the AE categories defined above. The number of TEAEs reported, the total number of years of study drug exposure, and the TEAE rate per 100 patient-years will be presented. For the SA_A and SA_C populations, 95% CI will be provided for the treatment differences between each upadacitinib group and placebo group. The treatment difference and 95% CI will be adjusted by the study size of the Phase 2b Induction Study and Induction Studies described by Sui et al.⁷

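### Protocol 6.1.4 closes adverse-event collection 30 days after the last dose, other sections imply collection to Week 52 for subjects who stay in Substudy 3 off drug, and planned outputs depend on which rule sites follow

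*Protocol*

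**What the plan says.** **The collection window.** Protocol 6.1.4 states: "All adverse events reported from the time of study drug administration until 30 days following discontinuation of study drug administration have elapsed will be collected". Its next sentence moves the start earlier for some events: "serious adverse events and protocol-related nonserious adverse events will be collected from the time the subject signed the study-specific informed consent". It sets no later end for serious events or deaths. Section 5.4.1 places the last telephone contact about adverse events roughly 30 days after the last dose, for all subjects.

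**Follow-up off drug.** The same Section 5.4.1 says that "subjects who prematurely discontinue study drug treatment should continue to be followed for all regularly scheduled visits", unless consent is withdrawn, and gives completeness of both efficacy and safety data as the reason.

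**Sections that point to longer collection.**
- Section 6.1 has investigators monitor adverse events for the duration of the study.
- Section 6.1.5 requires any serious event to be reported within 24 hours of site awareness and names no end date.
- Appendix E marks adverse-event monitoring at every Substudy 3 visit to Week 52/PD. Footnote r asks about UC hospitalisations and surgeries at each visit.
- Section 5.3.1.1 lists the hospitalisation and surgery (HCRU) forms among the outcomes completed at the Appendix C and E time points. Appendix G says these data "will be collected through subject Administration module SAE supplemental Page".

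**Planned outputs.**
- Substudy 3 SAP 9.2.2 splits deaths into those up to and those more than "30 days after last dose of study drug".
- Substudy 3 SAP 8.6 defines the UC hospitalisation and surgery estimand as the "difference in the incidence rate through Week 52 regardless of premature discontinuation of study drug or use of UC-related rescue medications".
- Protocol 8.1.8.2.1 promises: "The post-treatment AEs will be summarized in the same way as the treatment-emergent AEs described above".

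**The concern.** Section 6.1.4 is the only section written to define the collection period, so a site or monitor checking how long to record events will go there. Read literally, it lets a site stop recording 30 days after the last dose while the subject keeps attending visits. A site working from the Appendix E grid would record at every visit. Both could claim to follow the protocol.

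Three outputs then depend on which rule a site chose. The row for late deaths and the post-treatment summary could look complete while being under-ascertained. The hospitalisation and surgery estimand is defined to ignore drug discontinuation, so it needs the off-drug follow-up that 6.1.4 does not require.

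Subjects off drug but on study are an expected group. Protocol 6.1.7 addresses them explicitly, and Substudy 3 SAP 8.2.1 uses their efficacy data collected after stopping.

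**Working it through.** The plan states no figure for this gap, so there is nothing to reproduce. The check is date arithmetic plus a comparison of outputs with the window.

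**1. Length of the gap for one subject.** Inputs: closure 30 days after the last dose (Protocol 6.1.4); end of maintenance at Week 52, i.e. 52 × 7 = day 364 (Protocol 5.1.2); visits continue off drug (Protocol 5.4.1). With the last dose at week w:

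gap = 364 − (7w + 30) days, set to 0 if negative.

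| Last dose (week) | Literal closure (day) | Gap to Week 52 (days) |
|---|---|---|
| 4 | 28 + 30 = 58 | 306 |
| 12 | 84 + 30 = 114 | 250 |
| 20 | 140 + 30 = 170 | 194 |
| 28 | 196 + 30 = 226 | 138 |
| 36 | 252 + 30 = 282 | 82 |
| 44 | 308 + 30 = 338 | 26 |
| 48 | 336 + 30 = 366 | 0 |

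The gap vanishes at (364 − 30)/7 = 47.7, about Week 48. For a subject who stops at Week 12, closure falls at 114/7 = 16.3 weeks, so all five remaining scheduled visits (Weeks 20, 28, 36, 44 and 52) come after it.

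**2. Who is affected.** Subjects who stop before about Week 48, do not withdraw consent and do not enter M14-533. For those who enter M14-533, Substudy 3 SAP 9.2.1 runs the treatment-emergent window to their first dose there.

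**3. Outputs against the window.**
- Deaths more than 30 days after the last dose: every entry in this row lies beyond the 6.1.4 window.
- Post-treatment events: Protocol 8.1.8.2.1 excludes events starting more than 30 days after discontinuation from the treatment-emergent tables. Those are the events left for the post-treatment summary, and they too lie beyond the window. Substudy 3 SAP 9.2 contains no such summary, and the SAP's version history does not record dropping it.
- UC hospitalisation and surgery: the estimand runs to Week 52, but the data come on forms attached to adverse-event collection.

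**4. Time at risk.** Substudy 3 SAP 8.6 counts event-free subjects from Week 0 to the end of the 30-day follow-up, and subjects with an event from Week 0 to that event. Protocol 5.3.1.1 and Appendix E footnote c count the follow-up from the last dose. On that reading:
- An event-free subject whose last dose was at Week 12 contributes 84 + 30 = 114 days, against 364 in the estimand.
- The same subject, if hospitalised at Week 40 and recorded, contributes 40 × 7 = 280 days and one event.
- A completer without an event contributes about 364 + 30 = 394 days, past Week 52.

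So events may be counted after a point at which event-free subjects no longer contribute time, and the denominator does not match the estimand in either direction.

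**The case against.** The strongest reply is that 6.1.4 says what will be collected and does not bar later collection. Serious events have a start but no stated end in that section, and 6.1.5 requires their reporting with no cut-off. Off-drug subjects attend visits at which Appendix E schedules adverse-event monitoring and hospitalisation questions, and where the forms sit in the database does not import a 30-day limit. A row for deaths beyond 30 days suggests that the sponsor expected to have them. This stands, and it defeats the reading that later events are simply lost. It does not settle the conflict, because none of these sections says that it overrides 6.1.4 for subjects off drug. The content of Figure 5, to which 6.1.4 refers, was not available to me. If it shows a later end for serious events, the text should say so.

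A reader might also infer that the Substudy 3 SAP promises late malignancy, cardiovascular and thrombotic events. It does not: SAP 9.2.6 summarises events of special interest only as treatment-emergent. Only the general post-treatment sentence in Protocol 8.1.8.2.1 reaches later ones.

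Finally, a reader might infer that the subjects most harmed by the drug drop out of view. An event that itself leads to stopping falls inside the window, and Section 6.1 has it followed to a satisfactory conclusion.

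**Conclusion.** The point holds as an internal conflict with consequences for reported outputs. The protocol does not state one end date for serious events, deaths, events of special interest and hospitalisation forms once drug is stopped. A site that follows 6.1.4 would under-ascertain three outputs that the plan reports.

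The size per affected subject is firm under the literal reading: 250 days for a last dose at Week 12, 138 at Week 28, and none from about Week 48. The total is not known. A reader might multiply up: if 5 to 15% of 450 subjects (23 to 68) stayed on study off drug with 26 weeks left, the gap would be 26 − 30/7 = 21.7 weeks each, or 23 × 21.7/52.18 to 68 × 21.7/52.18, about 10 to 28 patient-years. The documents give neither that share nor that remaining time, and the sum assumes that every site follows 6.1.4 and ignores Appendix E. It illustrates a worst case and does not estimate a loss. A difference between arms is plausible, but the documents do not state one for this residual group.

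The change is worth making because the conflict is plain and the remedy is cheap.

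**What to change.** 1. **Protocol 6.1.4 and 5.4.1.** Reconcile them with 6.1, 6.1.5 and Appendix E. State that, for subjects off drug but still in the study, serious events, deaths, events of special interest and HCRU forms are collected to the later of the last study visit and 30 days after the last dose. Say that the day-30 call is additional to those visits and is not the final safety contact.
2. **Substudy 3 SAP 9.2.** Leave the treatment-emergent window unchanged. Report later events separately by arm as post-treatment events, as Protocol 8.1.8.2.1 promises.
3. **Substudy 3 SAP 8.6.** Align event-free time at risk with the Week 52 estimand: count it to Week 52, or to the end of actual follow-up if earlier, whether or not drug was stopped, and apply the same limit to the events counted.

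The cost is a short amendment, a form-completion instruction and a SAP edit. The visits, the monitoring row and the forms already exist. The downside is a few more post-treatment events to report, some arising on standard-of-care therapy. Substudy 3 enrolment is closed, so the amendment reaches prospectively only subjects still in follow-up. For the others, the report should say which collection rule their sites applied.

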6.1.5 Adverse Event Reporting

In the event of a serious adverse event, whether associated with study drug or not, the investigator will notify Clinical Pharmacovigilance within 24 hours of the site being made aware of the serious adverse event by entering the serious adverse event data into the electronic data capture (EDC) system. Serious adverse events that occur prior to the site having access to the RAVE[®] system, or if RAVE is not operable, should be documented on the SAE Non-CRF forms and emailed (preferred route) or faxed to Clinical Pharmacovigilance within 24 hours of the site being made aware of the serious adverse event.

Email: [contact]

FAX to: [contact]

For safety concerns, contact the Immunology Safety Team at:

Immunology Safety Team
[name]
[name]
[name]

Office: [contact]
Email: [contact]

For any subject safety concerns, please contact the physician listed below:

Primary Therapeutic Area Medical Director (TA MD):

[name]
[name]
United States

Office:
Cell:
Fax:
Email:

In emergency situations involving study subjects when the primary TA MD is not available by phone, please contact the 24-hour AbbVie Medical Escalation Hotline where your call will be re-directed to a designated backup AbbVie TA MD:

[contact]

AbbVie will be responsible for Suspected Unexpected Adverse Reactions (SUSAR) reporting for the Investigational Medicinal Product (IMP) in accordance with global and local guidelines and of the Investigator Brochure will serve as the Reference Safety Information (RSI). The RSI in effect at the start of a DSUR reporting period serves as the RSI during the reporting period. For follow-up reports, the RSI in place at the time of occurrence of the 'suspected' Serious Adverse Reaction will be used to assess expectedness.

In Japan, the principal investigator will provide documentation of all serious adverse events to the Director of the investigative site and the Sponsor.

COVID-19 Pandemic-Related Acceptable Protocol Modifications

Supplemental study case report forms should be completed in the event of COVID-19 related missed/virtual visits, study drug interruptions or discontinuations, or adverse events (including capture of specific signs/symptoms of infection and testing results).

COVID-19 infections should be captured as adverse events. If the event meets the criteria for a serious adverse event (SAE), then follow the SAE reporting directions per the protocol and above. The following COVID-19 related supplemental eCRFs should be completed:

- COVID-19 Supplemental Signs/Symptoms
- COVID-19 Status Form

If a subject has a confirmed or suspected COVID-19 infection and study drug was interrupted, the investigator should contact the sponsor emergency medical contact listed above before reintroducing study drug.

6.1.6 Pregnancy

Pregnancy in a study subject must be reported to AbbVie within 24 hours after the site becomes aware of the pregnancy. Subjects who become pregnant during the study must be discontinued (Section 5.4.1).

Information regarding a pregnancy occurrence in a study subject and the outcome of the pregnancy will be collected.

Pregnancy in a study subject is not considered an adverse event. The medical outcome for either mother or infant, meeting any serious criteria including an elective or spontaneous abortion, stillbirth or congenital anomaly is considered a serious adverse event and must be reported to AbbVie within 24 hours of the site becoming aware of the event.

6.1.7 Toxicity Management

The toxicity management of the AEs including AEs of special interest consists of safety monitoring (review of AEs on an ongoing basis, and periodic/ad hoc review of safety issues by an independent Data Monitoring Committee), and if applicable interruption of study drug dosing with appropriate clinical management and/or discontinuation of the subjects from study drug. The management of specific AEs and laboratory parameters is described below.

For subjects who discontinue study drug but continue study participation and are on standard of care therapies, these toxicity management requirements do not apply (including alerts from the central laboratory) and any intolerability to standard of care therapies should be managed by the prescribing physician.

Serious Infections: Subjects should be closely monitored for the development of signs and symptoms of infection during and after treatment with study drug. Study drug should be interrupted if a subject develops a serious infection. A subject who develops a new infection during treatment with study drug should undergo prompt diagnostic testing appropriate for an immunocompromised subject. As appropriate, antimicrobial therapy should be initiated, and the subject should be closely monitored. Study drug may be restarted once the infection has been successfully treated. These subjects will continue to be clinically monitored and will be evaluated in the safety analyses.

Subjects who develop active tuberculosis must be permanently discontinued from study drug (refer to "TB Testing/TB Prophylaxis" under Section 5.3.1.1).

Herpes zoster: If a subject develops herpes zoster, consider temporarily interrupting study drug until the episode resolves.

Gastrointestinal Perforation: Subjects presenting with the onset of signs or symptoms of a gastrointestinal perforation should be evaluated promptly for early diagnosis and treatment. If the diagnosis of spontaneous gastrointestinal perforation is confirmed (other

than appendicitis or mechanical injury), the subject must be permanently discontinued from study drug.

Cardiovascular Events: Subjects presenting with potential cardiovascular events including non-cardiac, non-CNS thrombotic and embolic events should be carefully monitored. These events will be reviewed and adjudicated by an independent Cardiovascular Adjudication Committee in a blinded manner.

Malignancy and Gastrointestinal (GI) Dysplasia: Subjects who develop malignancy other than nonmelanoma skin cancer (NMSC) or carcinoma in situ of the cervix, should be discontinued. Subjects who develop high grade colonic dysplasia, should be discontinued. Information including histopathological results should be queried for the confirmation of the diagnosis. Periodic skin examination is recommended for subjects who are at increased risk for skin cancer.

Thrombosis Events: Subjects who develop symptoms of thrombosis should be promptly evaluated and treated appropriately. If the diagnosis of deep vein thrombosis, pulmonary embolus or non-cardiac, non-neurologic arterial thrombosis is confirmed, the subject must be discontinued from study drug.

ECG Abnormality: Subjects must be discontinued from study drug for an ECG change considered clinically significant and with reasonable possibility of relationship to study drug.

Management of Select Laboratory Abnormalities: For any given laboratory abnormality, the investigator should assess the subject, apply the standard of care for medical evaluation and treatment and follow any local guidelines. Specific toxicity management guidelines for abnormal laboratory values are described in [Table 5](#), and may require a supplemental eCRF to be completed. All abnormal laboratory tests that are considered clinically significant by the investigator will be followed to a satisfactory resolution. If a repeat test is required per [Table 5](#), the repeat testing must occur as soon as possible.

Table 5. Toxicity Management Guidelines for Abnormal Lab Values

Hemoglobin	
 • If hemoglobin < 8.0 g/dL interrupt study drug dosing and confirm by repeat testing with new sample. • If hemoglobin decreases from Baseline ≥ 3.0 g/dL without an alternative etiology, interrupt study drug dosing and confirm by repeat testing with new sample. • If hemoglobin decreases ≥ 3.0 g/dL from Baseline and an alternative etiology is known or the hemoglobin value remains in the normal reference range, the subject may remain on study drug at the investigator's discretion. • If confirmed, continue to withhold study drug until hemoglobin value returns to normal reference range or its Baseline value.
Absolute neutrophil count (ANC)	
 • If confirmed < 1000 cells/μL by repeat testing with new sample, interrupt study drug dosing until ANC value returns to normal reference range or its Baseline value. • Interrupt study drug if confirmed < 500/μL by repeat testing with new sample. If value returns to normal reference range or its Baseline value, restarting study drug is allowed if there is an alternative etiology identified; documentation should include reason that rechallenge is expected to be safe for the subject. Study drug should be discontinued if no alternative etiology can be found.
Absolute lymphocyte count (ALC)	
 • If confirmed < 500 cells/μL by repeat testing with new sample, interrupt study drug dosing until ALC returns to normal reference range or its Baseline value.
Total white blood cell count	
 • If confirmed < 2000 cells/μL by repeat testing with new sample, interrupt study drug dosing until white blood cell count returns to normal reference range or its Baseline value.
Platelet count	
 • If confirmed < 50,000 cells/μL by repeat testing with new sample, interrupt study drug dosing until platelet count returns to normal reference range or its Baseline value.

Table 5. Toxicity Management Guidelines for Abnormal Lab Values (Continued)

AST or ALT	
 • Interrupt study drug immediately if confirmed ALT or AST $> 3 \times$ ULN by repeat testing with new sample and either a total bilirubin $> 2 \times$ ULN or an international normalized ratio (INR) > 1.5. 
 ○ A separate blood sample for INR testing will be needed to measure INR at the time of repeat testing for ALT or AST. A repeat test of INR is not needed for determination if above toxicity management criteria are met. • Interrupt study drug immediately if confirmed ALT or AST $> 3 \times$ ULN by repeat testing with new sample along with appearance of fatigue, nausea, vomiting, right upper quadrant pain or tenderness, fever, rash, and/or eosinophilia ($> 5\%$). • Interrupt study drug immediately if confirmed ALT or AST $> 5 \times$ ULN by repeat testing with new sample for more than 2 weeks. • Interrupt study drug immediately if confirmed ALT or AST $> 8 \times$ ULN by repeat testing with new sample. • Subjects with HBc Ab+ (irrespective of HBs Ab status) and negative HBV DNA PCR testing at screening who develop the following should have HBV DNA by PCR testing performed within 1 week (based on initial elevated value): 
 ○ ALT $> 5 \times$ ULN OR ○ ALT or AST $> 3 \times$ ULN if an alternative cause is not readily identified. 
 • A separate blood sample for HBV DNA PCR testing will be needed at the time of repeat testing for ALT or AST. 
A positive result for HBV DNA PCR testing in these subjects will require immediate interruption of study drug (unless not acceptable by local practices) and a hepatologist consultation should occur within one week for recommendation regarding subsequent treatment.
 
Subjects who meet any of the above criteria should be evaluated for an alternative etiology of the ALT or AST elevation and managed as medically appropriate. If applicable, the alternative etiology should be documented in the eCRF. If ALT or AST values return to the normal reference range or its Baseline value, study drug may be restarted. If restarting study drug, documentation should include reason that rechallenge is expected to be safe. If after clinically appropriate evaluation, no alternative etiology for ALT or AST elevation is found or the ALT or AST elevation has not resolved or is not trending down toward normal, the subject should be discontinued from study drug.
 
For any confirmed ALT or AST elevations > 3 ULN, complete supplemental hepatic eCRF

------------	---

Table 5. Toxicity Management Guidelines for Abnormal Lab Values (Continued)

Serum Creatinine (sCr)	
If serum creatinine is $> 1.5 \times$ the Baseline value and $> \text{ULN}$, repeat the test for serum creatinine (with subject in an euvoletic state) to confirm the results. If the results of the repeat testing still meet this criterion then interrupt study drug and restart study drug once serum creatinine returns to $\leq 1.5 \times$ Baseline value and $\leq \text{ULN}$. 
For the above serum creatinine elevation scenario, complete supplemental renal eCRF(s).

Creatine Phosphokinase	
If confirmed CPK value $> 4 \times \text{ULN}$ and there are no symptoms suggestive of myositis or rhabdomyolysis, the subject may continue study drug at the investigator's discretion.If CPK $> 4 \times \text{ULN}$ accompanied by symptoms suggestive of myositis or rhabdomyolysis, interrupt study drug and contact AbbVie TA MD.For above CPK elevation scenarios, complete supplemental CPK eCRF.

If the subject must undergo elective surgery, the study drug should be interrupted 1 week prior to the surgery. If the subject must undergo emergency surgery, the study drug should be interrupted at the time of the surgery. The study drug can recommence once the physician has examined the surgical site and determined that it has healed and there is no sign of infection.

Repeat testing must be performed by central laboratory.

